#### **12.2.2.9. Final On-Study Evaluations**

Subjects who elect to discontinue medication will be asked to comply with end of study assessments (see visit 4 on schedule of activities table) at a follow-up visit in an outpatient setting (to be determined by Investigator or Staff) at 7 +/- days after the last treatment visit. Subjects who withdraw due to an adverse event will be followed whenever possible until resolution of the adverse event. It may be appropriate for the subject to return to the site 2 weeks after the subject is off study to evaluate for resolution of any adverse events and to

---

#### **CONFIDENTIAL INFORMATION**

The information in this study protocol is confidential. Any disclosure, copying or distribution of the information contained within is strictly prohibited without written consent from University of Florida.

receive further information about options for future clinical care. The Investigator will decide the course of action.

#### **12.2.2.10. Off-Study Requirements**

Study medication will be distributed at Week 24 (due to COVID-19 pandemic and travel difficulties). Drug will be discontinued and collected at Week 36. Study drug will be ordered by the Co-Investigator, dispensed by Investigational Drug Service and a study team member will ship it to the participants (3). There are no additional risks of extending the medication by 12 weeks. The subject will be contacted by phone at weeks 18 and 36 to evaluate for resolution of any adverse events and to receive further information about options for future clinical care. In addition to this contact there will be another phone contact at weeks 36 and 52 to monitor long term health and follow-up on clinical outcome. This phone call will be at the discretion of the Investigator. Subjects may be contacted for follow-up safety evaluations, including possible blood draw for further study.

#### **12.2.2.11. Pregnancy**

Women who are pregnant will not be enrolled in the study. Metformin has not been well studied in pregnancy and the Metformin US Package Insert notes that based on animal studies Metformin was not teratogenic. A recent review of RCT data reveal no evidence of an increase in congenital malformations or miscarriages when Metformin is started before pregnancy and continued to term (Hyer et al 2018).

Following administration of study drug, any known cases of pregnancy in female subjects or female partners of male subjects, will be reported until 30 days after the subject completes or withdraws from the study. (Section 13.3; *Procedures for Reporting Adverse Events*)

### **12.3. SPECIAL INSTRUCTIONS AND DEFINITIONS OF EVALUATIONS**

#### **12.3.1. Protocol Deviations**

Missed visits and any procedures not performed (not attempted) for any reason will be reported as protocol deviations. Details regarding any deviations will be documented.

#### **12.3.2. Documentation of Amyotrophic Lateral Sclerosis**

To be eligible for participation in this trial, participants must have ALS defined as probable or definite ALS in accordance with the Revisited El-Escorial Criteria (Cedarbaum,1999). These criteria will be clearly designated on source documentation and in the electronic case report forms (eCRFs).

---

### **12.3.3. Medical History**

A comprehensive medical history will be obtained at the screening visit and reviewed for any exclusionary criteria.

### **12.3.4. Treatment History**

Medications will be reviewed for concomitant therapies that would be exclusionary.

### **12.3.5. Concomitant Medications/Treatments**

Current medications will be reviewed for contraindicated therapies.

### **12.3.6. Clinical Assessments**

Patient Reported Outcomes: The Eating Assessment Tool 10^91 (**Appendix B**) and the ALSFRS-R (Appendix A) will be administered at each time point to track self-reported bulbar impairment profiles. To facilitate efficiency, questionnaires will be sent to patient's homes one-week prior to appointments for completion.

### **12.3.7. Laboratory Evaluations**

Blood specimens will be collected by qualified study center personnel at Screening, Visit 1, 2, 3, and Visit 4 as described under study procedures and sent to Shands for analysis for the following safety laboratory evaluations: hematology (complete blood count with differential), chemistry (electrolytes, BUN, creatinine, ALT, AST, total bilirubin, albumin). Urine will be collected for urinalysis.

In females, of childbearing potential, urine will be collected for pregnancy test during recruitment/screening, visit 1, visit 3 and visit 4. Prior to each VFSS, women of childbearing potential will be asked to perform the urine pregnancy test in a private bathroom located near the exam room.

C9orf72 testing will be performed using the repeat-primed PCR assay and other molecular assays as needed in the [name] lab.

RAN protein levels: Isolation of peripheral blood lymphocytes (PBLs) for protein and other molecular studies will be performed in the [name] and the [name] laboratories. C9 RAN proteins present in the blood will be analyzed using highly sensitive MesoScale Discovery (MSD) electrochemiluminescence assays using custom antibodies generated and characterized by the [name] group. The MSD assays has been optimized for the detection of C9 RAN proteins. The remainder of the samples will be stored in the Center for NeuroGenetics bank for additional molecular or biochemical studies for an indefinite period of time.

---

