## 6.4. Safety

Metformin is contraindicated in patients with severe renal impairment (eGFR below 30 mL/min/1.73 m^2), hypersensitivity to Metformin, and acute or chronic metabolic acidosis, including diabetic ketoacidosis, with or without coma.

See attached product information sheet (Appendix H) regarding the warnings and precautions (lactic acidosis, vitamin B12 deficiency, and hypoglycemia).

The most commonly observed AEs associated with the use of Metformin are listed in table 1 of the product information sheet and include diarrhea, nausea/vomiting, flatulence, asthenia, indigestion, abdominal discomfort, and headache. Diarrhea lead to discontinuation in 6% of patients.

Postmarketing experience has identified cholestatic, hepatocellular, and mixed hepatocellular liver injury (see package insert attached).

---

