## **9.2. Study Enrollment Procedures**

The following screening procedures will be conducted on each potential subject.

- Obtain informed consent as evidenced by potential subject or subject's legally authorized representative signing an informed consent. Informed consent will be signed prior to any study-related procedures and prior to screening per protocol. Informed consent will be obtained by one of the investigators and/or his or her designee.
- Record medical history
- Documentation of disease and C9orf72 mutation
- Obtain vital signs (temperature, respiratory rate (RR), heart rate (HR), blood pressure (BP)) and weight/height.
- Collect blood and urine for clinical laboratory evaluation (hematology, chemistry, liver function tests, urinalysis) and for additional molecular studies including RAN protein assessment, and urine for pregnancy test (females of childbearing potential only). For a complete list of all tests to be performed (Section 12.3.7, *Laboratory Evaluations*.)

---

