#### **9.2.1. Subject Recruitment and Retention**

Details for recruitment procedures are provided in the protection of human subjects section. Briefly, ALS patients will be primarily identified and recruited from the University of Florida-Gainesville. Due to the rarity of the C9orf72 gene mutation, if insufficient patients are recruited, physicians at the University of Florida we are in frequent contact with physicians at other ALS centers in Florida and other parts of the US (Mayo-JAX, UF Jacksonville, Baptist Health, USF, and Miami, Johns Hopkins and Washington University) or other institutions and organizations. Generally, patients with the C9orf72 gene are well-known to their attending neurologists. The PI, co-investigators, and study coordinator will be able to work with treating neurologists at these sites to identify potential participants. C9 ALS subjects currently taking Metformin or previously prescribed Metformin may be considered. If a patient known to have the C9orf72 mutation is interested, contact information will be offered to the patient so that they can communicate with local study staff at will. We have a target recruitment schedule of only 16 patients and it is expected that there will be minimal need to reach out to other sites. All other sites, if referring patients, will ONLY BE USED FOR RECRUITMENT purposes. All recruited patients will be seen at UF Gainesville. The study will be advertised through clinicaltrials.gov and IRB approved UF listings.

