**Table 3. Schedule of Activities:**

Evaluation	Recruit & Screen	Visit 1	Visit 1	Visit 2	Visit 3	Phone Call	Visit 4	Visit 4	Phone Call	Phone Call
		Day 1	Day 2	6 weeks	12 weeks	18 Weeks	Day 1 24 weeks	Day 2 24 weeks	36 Weeks	52 weeks
		PM	AM	(42 days)	(84 days)	(126 days)	(168 days)	(168 days)	(252 days)	(365 days)
Informed Consent	X									
Inclusion/Exclusion Review	X									
Documentation of Disease	X									
Record/Review Concomitant Medications	X		X	X	X	X	X		X	
Medical History/Demographics	X		X			X				X
Vital Signs/Height and Weight	X		X	X	X		X			
Comprehensive Physical and Neurological Exams	X				X		X			
Brief Physical and Neurological Exam			X	X						
C9+ and RAN protein blood draw	X		X	X	X		X			
Clinical Labs for safety (hematology, chemistry, liver function and urinalysis)	X		X	X	X		X			
Urine Pregnancy Test (females of childbearing potential)	X		X	X	X		X			
Lumbar Puncture (for RAN proteins and biomarkers)			X	X	X		X			
MRI/DTI imaging			X					X		
VFSS Penetration-Aspiration Scale		X			X			X		
Functional Oral Intake Scale (FOIS)		X			X	X		X	X	X
ALS Functional Rating Scale – Revised (ALSFRS-R)	X		X	X	X	X	X		X	X
Eating Assessment Tool-10 (EAT-10)		X			X	X		X	X	X
Forced Vital Capacity (FVC)		X			X			X		
Peak Cough Flow		X			X			X		
Body Mass Index		X			X			X		
BDI-FastScreen	X			X	X		X			
Adverse Event			X	X	X	X	X		X	X
Dispense Study Drug			X	X	X					

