### 12.2.1. Screening procedures

At the screening visit, potential subjects will be informed about study procedures and will then sign an informed consent form. Inclusion/exclusion criteria will be reviewed and a medical history and comprehensive physical and neurological examination will be completed. Vital signs, height, weight, and concomitant medications will be recorded. Safety laboratory tests will be performed including complete blood count (CBC) with differential, electrolytes, BUN, creatinine, ALT, AST, total bilirubin, albumin, and a urine pregnancy test for women of childbearing potential. and COVID-19 nasal collection and testing.

The following procedures will be performed during the screening visit:

- Informed consent
- Inclusion/exclusion assessment

---

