As part of the screening visit, the investigator will determine the competence of caregiver to administer the study drug at home. Teaching will begin on the importance of compliance and proper handling of study drug. All inclusion and exclusion criteria and safety laboratory tests will be reviewed by the investigator prior to scheduling the baseline visit (visit 1 on schedule of activities table). A paper log will be kept at the site to record all subjects screened for entry into the study. This information will also be captured electronically in the electronic data capture system (EDC) using REDCap. REDCap (Research Electronic Data Capture) is a secure, Web-based application designed to support traditional case report form data capture. Demographic characteristics of all subjects who are screened will be recorded whether or not they qualify for entry into the study. The reason for non-qualification will be recorded for all subjects who are not eligible. The reason for nonparticipation will also be recorded for subjects who are eligible but choose not to participate in the trial. If a subject fails screening for the study, the subject can be re-screened if the investigator determines it is appropriate to do so. At any time during the study, repeat laboratory tests can be obtained if the investigator or central laboratory believes that a laboratory test result is in error. Additional laboratory tests may also be obtained at any time during the study, at the discretion of the investigator.

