#### **12.2.2.5. Study Visit 4, Week 24 Day 1 or Day 2:**

All subjects will return at week 24 for a two-day end of study evaluation. The visit window is to be scheduled at 24 weeks (168 days) plus or minus 3 days. Participants will be seen for assessment of any adverse events, and concomitant medications. Study drug accountability and compliance will be assessed. Vital signs, physical and neurologic examination, as well as study questionnaires and testing will be performed as noted in the schedule of activities.

The following documentation and procedures will be performed at Visit 4, Week 24, on Day 1 or Day 2:

- Adverse events
- Record/review concomitant medications
- Vital signs, weight and height
- ALSFRS-R
- Comprehensive physical exam
- Comprehensive neurologic exam
- Clinical labs for safety (hematology, chemistry, liver functions, and urinalysis) – Due to the COVID-19 Pandemic, and only for the participants currently enrolled (3) in this study, the clinical labs for safety will be drawn at a local lab or physician's office and will be shipped as needed. If there is any charge for the draw the participant may either pay the invoice and be reimbursed or have the lab contact the study team in the ICF to pay the invoice directly. This modification to the protocol is to prevent potential exposure to COVID-19 by minimizing participant travel to our site.
- Blood draw for C9+ and RAN proteins – Due to the COVID-19 Pandemic, and only for the participants currently enrolled (3) in this study, additional blood samples will be collected and will be shipped to the [name] Lab for analysis. The kits, drawing instructions, and shipping documents will be sent to the physician or the participant to complete this procedure. If there is a charge for the blood draw the participant may either pay the invoice and be reimbursed or have the lab contact the study team in the ICF to pay the invoice directly. This modification to the protocol is to prevent potential exposure to COVID-19 by minimizing participant travel to our site.
- Urine Pregnancy Test (females of childbearing potential)
- COVID-19 nasal collection and testing may take place at this visit if travel time allows for the participant - Due to COVID-19 Pandemic, nasal collection and testing of the participants has been implemented to determine if the participant is COVID

---

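### The scheduled safety panel includes neither blood glucose nor vitamin B12, although the protocol names hypoglycemia and B12 deficiency as metformin warnings and safety is the primary objective

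*Combined protocol and SAP*

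**What the plan says.** Section 6.4 refers the reader to the product sheet "regarding the warnings and precautions (lactic acidosis, vitamin B12 deficiency, and hypoglycemia".

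Section 12.3.7 lists the safety laboratory work: a blood count with differential, "chemistry (electrolytes, BUN, creatinine, ALT, AST, total bilirubin, albumin", and urinalysis. Section 9.2 cites Section 12.3.7 with the words "For a complete list of all tests to be performed". Section 12.2.1 repeats the same blood analytes for screening: "electrolytes, BUN, creatinine, ALT, AST, total bilirubin, albumin, and a urine pregnancy test". Table 3 and the visit lists give only categories: "Clinical Labs for safety (hematology, chemistry, liver function and urinalysis". Table 3 schedules these labs at Screening, Visit 1 (Day 2), Visit 2, Visit 3 and Visit 4.

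Three other provisions bear on the point:

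- Section 12.2.1 allows extra testing: "Additional laboratory tests may also be obtained at any time during the study, at the discretion of the investigator".
- Section 9.2.1 opens the trial to people with earlier exposure: "C9 ALS subjects currently taking Metformin or previously prescribed Metformin may be considered".
- Section 12.2.2.5 moves some Visit 4 labs off site: "only for the participants currently enrolled (3) in this study, the clinical labs for safety will be drawn at a local lab". The synopsis (Interventions) adds safety labs near home for subjects who stay on drug from Week 24 to Week 36, without saying what they contain.

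**The concern.** Safety and tolerability are the primary objective, and Section 15.3 lists clinical laboratory tests among the outcomes to be summarised. The protocol itself names the metformin risks it regards as warnings, yet for two of them it schedules no direct measurement. If sites do exactly what is written, the final safety summary can say nothing direct about glucose or B12.

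The baseline is the most important part. Someone already taking metformin, or who took it before, may enter with a low B12. Without a value before the first study dose, a low result on study cannot be separated from that earlier exposure.

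Section 12.2.2.10 also states that twelve more weeks of drug carry no added risk. That is 36/24 = 1.5 times the planned exposure. For B12 and glucose, the listed tests could not check the statement.

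**Working it through.** **Cross-check of the named warnings against the panel.** No plan figure needs reproducing. The first step sets Section 6.4 beside Sections 12.2.1 and 12.3.7.

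| Warning in Section 6.4 | Direct test listed | Indirect cover |
|---|---|---|
| Hypoglycemia | None (no blood glucose) | Adverse event review; Section 11.2.2 bars drugs affecting glucose control |
| B12 deficiency | None | Blood count at each safety draw |
| Lactic acidosis | No lactate; bicarbonate only if it is part of the electrolytes, which is not stated | Exclusions for eGFR below 30 and for hepatic impairment; repeat creatinine and BUN; Section 11.2.2 |

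Elsewhere, glucose occurs only in the drug-interaction text and B12 only in the warning itself. The components of the urinalysis are not given, and urine glucose would not detect hypoglycemia.

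**Number of assays if both were added.** Inputs: 16 subjects (Section 8); five scheduled draws each (Table 3), or four when Screening and Visit 1 fall in the same week and the labs are not repeated (Section 12.2.2.1).

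- Glucose, all 16 under the amended list: 16 x 5 = 80, or 16 x 4 = 64.
- B12, two each: 16 x 2 = 32.

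Section 12.2.2.5 describes three subjects already enrolled whose Visit 4 is being handled locally. Assume they have no stored baseline and contribute Visit 4 only, which leaves 16 - 3 = 13 with a baseline:

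- Glucose: 13 x 5 + 3 = 68, or 13 x 4 + 3 = 55.
- B12: 13 x 2 + 3 = 29.
- If three subjects give a Week 24-36 sample (the number in Section 12.2.2.10), B12 rises to 35 or 32.

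**What the data would support.** The half-width of a 95% confidence interval for a mean change, in units of the SD of change, is t(0.975, n-1)/sqrt(n):

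- n = 16: 2.131/4 = 0.53 SD
- n = 13: 2.179/3.606 = 0.60 SD

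If no subject developed a low B12, the one-sided 95% upper bound on the rate is 1 - 0.05^(1/n):

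- n = 16: 17.1%
- n = 13: 20.6%

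These figures assume complete pairs; dropout widens all of them.

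**The case against.** The strongest reply is that the plan is not blind to these risks. Adverse events are reviewed at Visits 1 to 4 and by telephone at Weeks 18, 36 and 52, so symptomatic events have a route to capture. Section 9.1.2 excludes eGFR below 30, which Section 6.4 gives as a metformin contraindication, and also excludes hepatic impairment. Creatinine and the blood count are repeated. Interacting drugs are barred, clinically important abnormal results are followed, and an external physician acts as safety monitor. All of that stands. It reduces the weight of the point, but none of it measures glucose or B12.

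A reader might infer that no baseline can exist. The documents do not support that. The permission for extra tests sits in the screening section and applies at any time, so B12 could be ordered before dosing. Section 12.3.7 also banks leftover blood, although it does not say whether suitable serum or plasma is kept. What is missing is a guarantee of a baseline and a uniform series.

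A reader might also infer that acid-base status goes unmonitored. That is not shown either: electrolytes may already include bicarbonate, and the protocol simply does not say.

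Two further replies are fair. The precision figures follow from the sample size alone and would be the same for any unlisted analyte; they show what could be learned, not the size of any harm. And safety is summarised descriptively without formal tests, so no primary test depends on these assays.

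**Conclusion.** The gap is real but modest. The scheduled panel has no direct test for two of the three metformin risks named in Section 6.4, in a trial whose primary objective is safety. It should be closed because closing it is cheap.

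It would be tempting to call this a breach of the drug's labelling. The documents do not support that: the product sheet (Appendix H) is not reproduced, and nothing in the text says that serial glucose or B12 testing is required.

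The main gain is an estimate of B12 and glucose change from baseline, with a half-width of 0.53 SD (16 pairs) or 0.60 SD (13 pairs), where the present plan gives none. Spot samples would rarely catch transient hypoglycemia or rare lactic acidosis. The documents give no rate or time course for B12 decline over 24 to 36 weeks, so the clinical size of the problem cannot be stated. The figure of 13 assumes that the three subjects in Section 12.2.2.5 have no usable stored baseline.

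**What to change.** 1. Sections 12.2.1 and 12.3.7: add glucose to the chemistry list at each scheduled safety draw.
2. Add vitamin B12 before the first study dose (Screening or Visit 1), at Visit 4 or the early-discontinuation visit, and at the last Week 24-36 safety draw for subjects who continue study drug. Flag early-discontinuation values as off drug, since Section 12.2.2.8 places that visit about 14 days after the last dose.
3. Apply the same list to local Visit 4 labs and to the Week 24-36 labs.
4. Section 15: summarise observed values and change from baseline, and identify current or past metformin users. List subjects without a baseline separately, with no change score, unless suitable banked samples exist.
5. As a clarification only, state that electrolytes include bicarbonate. Leave lactate to clinical suspicion. A fixed bicarbonate trigger has no basis in the documents. If the laboratory's lower limit cuts off 2.5% of normal values (an assumption), 64 to 80 draws would give 0.025 x 64 = 1.6 to 0.025 x 80 = 2.0 chance flags.

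Cost: assay fees for 55 to 80 glucose and about 29 to 35 B12 measurements, plus chemistry on the Week 24-36 labs, whose number is not stated. The documents give no prices. Some incidental abnormal values will need follow-up under Section 12.3.7. No extra scheduled visit is needed.

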## Experimental Design

This is a single-center, open label safety and tolerability trial. Approximately sixteen (16) individuals with C9orf72 amyotrophic lateral sclerosis (ALS) will be enrolled. Subjects will be screened to determine eligibility according to the specified inclusion/exclusion criteria. Following informed consent, screening, and enrollment, during study visit 1, subjects will undergo clinical examinations and questionnaires including the validated amyotrophic lateral sclerosis functional rating scale-revised (ALSFRS-R). Subjects will have blood work performed to monitor clinical safety, RAN proteins and biomarker analyses. Lumbar punctures will be performed to allow measurements of RAN protein levels in the cerebrospinal fluid (CSF) and for molecular and biomarker analyses. MRI/DTI imaging will be obtained at the beginning of the study and at the end of the drug treatment phase. Subjects will return on Day 1 for swallowing and respiratory evaluation. The subjects will then be given a first dose of Metformin (with escalating dose of the drug. The initial dose during week one will begin at 500mg/day, in the following weeks this will increase to 1000 mg/day (week two), 1500 mg/day (week three) and 2000mg per day (weeks 4 to 24). The subjects will begin by taking the first dose in the morning during week one and then morning and evening doses in weeks 2-24 with an interim assessment at days 42, 84 and final evaluation at 168 days (+/- ~7) to assess the safety and tolerability of Metformin.

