**CONFIDENTIAL INFORMATION**

The information in this study protocol is confidential. Any disclosure, copying or distribution of the information contained within is strictly prohibited without written consent from University of Florida.

Inclusion Criteria

1. Male or female subjects between 18-80 years of age, inclusive.
2. Subjects have a diagnosis of probable or definite ALS in accordance with the Revisited El-Escorial Criteria (Cedarbaum, 1999).
3. Subjects have a diagnosis of C9orf72 positive ALS.
4. Subjects must be currently on an oral diet and able to take foods, pills and liquids by mouth equivalent to a score of 4 or above on the Functional Oral Intake Scale (Crary, 2005).
5. Subjects must have no known allergy to Metformin.
6. Subjects or subject's legally authorized representative must be willing and able to complete informed consent/assent and HIPAA authorization.
7. Ability of the study subject or representative to comprehend and be informed of the nature of the study, as assessed by the PI or Co-Investigators.
8. Availability to participate for the entire study duration.
9. Female subjects of childbearing potential must have a negative urine pregnancy test prior to a videofluoroscopic swallowing study (VFSS) exam during Visit 1, 3, and 4.

---

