#### CONFIDENTIAL INFORMATION

The information in this study protocol is confidential. Any disclosure, copying or distribution of the information contained within is strictly prohibited without written consent from University of Florida.

5. Subjects or subject's legally authorized representative must be willing and able to complete informed consent/assent and HIPAA authorization.
6. Ability to comprehend and be informed of the nature of the study, as assessed by the PI or Sub-Investigator.
7. Availability to participate for the entire study duration.
8. Female subjects of childbearing potential must have a negative urine pregnancy test at Screening and Visit 1, 3, and 4.

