### **12.2.2. On-Study/On-Intervention Evaluations/Procedures**

#### **12.2.2.1. Baseline, Visit 1, Day 1 pm and Visit 1, Day 2 am:**

The baseline visit (Visit 1, Day 1 pm and Visit 1, Day 2 am), will cover 2 days and include the first dose of study drug, and study drug dispensing. It will be scheduled within 14 to 28 days after the screening visit. At this visit inclusion/exclusion criteria and concomitant medications will be reviewed. Vital signs, brief physical and neurologic examination, as well as study questionnaires and testing will be performed as noted in the schedule of activities. To lessen travel for participants during the COVID-19 pandemic, and after the pandemic, the Visit 1, Day 1 and Visit 1, Day 2 may take place in the same week as the Screening visit. If these visits are scheduled to take place in the same week, the \*clinical labs for safety and \*blood draw for C9+ and RAN proteins, and \*urine pregnancy test, will not be repeated.

The following documentation and procedures will be performed at Baseline (Visit 1, Day 1):

---

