#### **CONFIDENTIAL INFORMATION**

The information in this study protocol is confidential. Any disclosure, copying or distribution of the information contained within is strictly prohibited without written consent from University of Florida.

- FOIS
- BDI-Fast Screen (BDI-FS)
- VFSS – Penetration Aspiration Scale
- EAT – 10
- Forced Vital capacity (FVC)
- Peak Cough Flow
- Body Mass Index

The following documentation and procedures will be performed at Baseline (Visit 1, Day 2):

- Adverse event review
- Inclusion/exclusion assessment
- Record/review Concomitant medications
- Medical history
- Vital signs; weight and height
- Brief physical exam
- Brief neurologic exam
- Clinical labs for safety (hematology, chemistry, liver functions, and urinalysis)
- Blood draw for C9+ and RAN proteins
- Lumbar puncture for RAN proteins and biomarkers
- Urine Pregnancy Test (females of childbearing potential)
- MRI/DTI imaging
- ALSFRS-R
- Dispense study drug

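### At Visit 1 the swallowing fluoroscopy is scheduled the afternoon before the pregnancy test that must precede it, the same-week option drops that test, and section 9.1.1 alone admits possible ALS

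*Combined protocol and SAP*

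**What the plan says.** Several places require the pregnancy test to come first, or to be done at the VFSS visit:

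- Synopsis, inclusion criterion 9: women of childbearing potential "must have a negative urine pregnancy test prior to a videofluoroscopic swallowing study (VFSS) exam during Visit 1, 3, and 4".
- Section 12.3.7: "Prior to each VFSS, women of childbearing potential will be asked to perform the urine pregnancy test", in a bathroom close to the exam room.
- Section 9.1.1, criterion 8: they "must have a negative urine pregnancy test at Screening and Visit 1, 3, and 4".
- Section 13.3: a negative test is needed at every visit with a VFSS.

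The schedule differs. In Table 3 the row "VFSS Penetration-Aspiration Scale" is marked at Visit 1 Day 1 PM, Visit 3 and Visit 4 Day 2. The pregnancy test row is marked at screening, Visit 1 Day 2 AM, Visit 2, Visit 3 and Visit 4 Day 1. The lists in section 12.2.2.1 repeat the Visit 1 arrangement, with the VFSS under Day 1 and the pregnancy test only under Day 2.

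On timing, section 12.2.2.1 says of the baseline visit: "It will be scheduled within 14 to 28 days after the screening visit". It also allows Visit 1 in the same week as screening, in which case the "urine pregnancy test, will not be repeated".

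On diagnosis, section 9.1.1 criterion 2 accepts possible, probable or definite ALS. The synopsis (study population entry and inclusion criterion 2) and section 12.3.2 accept only probable or definite.

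**The concern.** The design intent is clear: no fluoroscopy for a woman of childbearing potential until a pregnancy test has cleared her. Staff running a baseline visit work from the schedule table and the visit list, and here both put the exposure first. A positive result the next morning would exclude her under exclusion criterion 6, but only after she had been irradiated. On the same-week path there may be no Visit 1 result at all.

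The ALS mismatch is unrelated to fluoroscopy but is the same kind of fault. A patient with possible ALS is eligible under section 9.1.1 and ineligible under section 12.3.2, and the visible text does not say which governs. With about 16 subjects, one such enrolment is 1/16 = 6.25% of the cohort. Whether it counts as an eligibility deviation would depend on the section consulted.

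**Working it through.** There is no sample-size, power or error-rate figure here, so the check is a side-by-side reading plus a few counts.

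**Step 1. Order at each VFSS visit, from Table 3.**

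| Visit | VFSS | Pregnancy test | Order |
|---|---|---|---|
| Visit 1 | Day 1 PM | Day 2 AM | Test after exposure |
| Visit 3 | Week 12 | Same day | Order left to 12.3.7 |
| Visit 4 | Day 2 | Day 1 | Test before exposure |

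The order fails at 1 of 3 VFSS visits. The Visit 1 entry is not a table-extraction fault, because the prose lists in 12.2.2.1 give the same days and that section names Day 1 as afternoon and Day 2 as morning. For Visit 4, section 12.2.2.5 lists all procedures under either day without fixing an order, so the acceptable result there rests on Table 3 and the general rule in 12.3.7.

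The synopsis (Experimental Design) says "Subjects will return on Day 1 for swallowing and respiratory evaluation". That agrees with the day given for the VFSS. It comes after a description of the other Visit 1 procedures, however, so it does not settle the sequence and I do not rely on it.

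**Step 2. Age of the last scheduled test at the Visit 1 VFSS.**

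- Standard path: the last earlier test is at screening, and baseline follows 14 to 28 days later. Age = 14 to 28 days. The Visit 1 test comes the morning after the exposure.
- Same-week path: the documents do not define a week. If it means within 7 calendar days, age is at most 7 − 1 = 6 days.

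**Step 3. Number of scheduled tests, from Table 3.**

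- Standard path: screening, Visit 1, Visit 2, Visit 3, Visit 4 = 5.
- Same-week path: 5 − 1 = 4, with none at Visit 1.

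Section 12.3.7 omits the Visit 2 test. On that list the totals are 4 and 3, and the Visit 1 count still falls from 1 to 0.

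**Step 4. Which rules each path breaks.**

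- Standard path: a Visit 1 test is done, but after the VFSS. This breaks the ordering rule in 12.3.7 and in synopsis criterion 9, unless a screening test 14 to 28 days old is accepted as the prior test.
- Same-week path: no Visit 1 test is done. This conflicts with 9.1.1 criterion 8, with 13.3, and with the test-before-each-VFSS rule in 12.3.7.
- Exclusion criterion 6 uses the Visit 1 result. That result is late on the first path and absent on the second.

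**Step 5. ALS certainty.** Four statements were compared: 9.1.1 criterion 2, the synopsis population entry, synopsis inclusion criterion 2, and 12.3.2. One includes possible ALS and three do not.

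**The case against.** The strongest reply is that no woman reaches the first VFSS untested. Screening includes a urine pregnancy test, section 12.2.1 has the investigator review all criteria and safety laboratory results before baseline is scheduled, and section 12.2.2.11 bars enrolment of pregnant women. On the same-week path the screening test is only days old and does precede the VFSS. Synopsis criterion 9 can then be read as met, and exclusion 6 can be applied to the screening result. That path is in fact safer on timing than the standard one. Finally, 12.3.7 is never revoked, so staff who follow it literally would test beside the exam room whatever the table shows.

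Much of this stands as a limit on the harm. The residual risk is a pregnancy that begins, or becomes detectable, between the screening test and the VFSS, and it arises only where staff follow the schedule rather than 12.3.7. It does not remove the contradiction. The protocol asks for a test before each VFSS and for a negative result at Visit 1, and a screening test up to 28 days old meets neither requirement. Nor does the text say that 12.3.7 overrides the same-week exemption.

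It is also fair to say that these are clerical mismatches with a stated intent rather than a flawed design choice, and that the ALS point is a one-word difference. That affects how easy they are to correct, not whether they should be.

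**Conclusion.** The point holds and should be corrected. At Visit 1, one of three VFSS visits by Table 3, the scheduled exposure precedes the Visit 1 pregnancy test. The last test beforehand is 14 to 28 days old on the standard path, or at most about 6 days old on the same-week path if a week means 7 calendar days. On the same-week path, Visit 1 tests fall from 1 to 0 if section 12.2.2.1 is followed as written. On ALS certainty, one of four statements disagrees with the other three.

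The documents do not give the number of women of childbearing potential or the share of candidates with possible ALS, so the number of people affected cannot be estimated. No effect on a planned analysis is claimed.

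**What to change.** - **Table 3:** move the Visit 1 urine pregnancy test from Day 2 AM to Day 1 PM and label it as preceding the VFSS.
- **Section 12.2.2.1:** move the test from the Day 2 list to the top of the Day 1 list, and remove it from the items not repeated under the same-week option.
- **Section 9.1.1, criterion 2:** restrict to probable or definite ALS, matching the synopsis and 12.3.2. If possible ALS is intended, amend those three statements instead.

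Two wording items can be tidied in the same amendment, though the conclusion does not depend on them. Criterion 3 of 9.1.1 omits the ability to take pills, which the synopsis includes. Exclusion 9 refers to moderate or severe renal impairment but uses the eGFR cut-off of 30 that section 6.4 gives for severe impairment only; the clinical team should choose the threshold.

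Cost: on the standard path, no extra test, only an earlier one. On the same-week path, one extra urine test per woman of childbearing potential. A Day 1 test still precedes drug dispensing on Day 2. Keeping the narrower ALS definition may slightly reduce the number of eligible patients.
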